2. Patients seeking care in the UCHealth system, who may receive an opioid prescription. The population will be limited to non-prisoners 12-89 years of age. Individuals with an active cancer diagnosis, sickle cell disease, or receiving specific end of life care are excluded. Pregnant women and decisionally challenged people will be included but are not considered a target population. No efforts will be made to include these individuals. Patients with limited literacy or limited English fluency will be included but are not considered a target population. Juveniles seen at providers included in the specialties of interest will be included (ages 12-17 inclusive) due to the inclusion of their health care provider. On the advice of pediatric toxicology experts, a cut point of 12 years of age is a clinically relevant age at which misuse of opioid analgesics and other controlled medications becomes a notable risk. However, no efforts will be made to target or enhance inclusion of juveniles. Pediatrics-only specialist offices will not be included in rollout of the CDS tools. Outcomes measures from juveniles will be examined separately from adults but may be included in the overall population if statistically appropriate.

C. Study Design and Research Methods

This will be a 1) cluster-randomized (by practice, as identified by a group of providers who work in the same department or set of departments within UCHealth) study for ambulatory/outpatient providers and 2) a randomized study (by provider) for emergency medicine and inpatient providers, with four study arms:

1. Arm 1: No change in practice
 - Providers are free to access the PDMP when prescribing via the existing integrated PDMP button.
 - This control group will enable monitoring of the secular changes in rates of controlled medication prescription within the UCHealth system.
 - In order to facilitate analysis of patient outcomes, CDS logic as in group 4 will run “silently” in this group such that risks are identified and recorded but not seen by the provider.
2. Arm 2: “Mandatory” use of the PDMP for all opioid prescriptions.
 - A best practice alert (BPA) will be triggered and fire when ordering an opioid prescription. The BPA will not appear (i.e. it will be suppressed) if the provider already reviewed the PDMP within the encounter. The BPA is shown in Figure 2 below.

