- The CDS will fire based on the same characteristics as in Group 3 OR if clinical history characteristics recorded in the EHR indicate increased high-risk. Again, these risk factors have been determined based on work with providers and include risk factors based on prior published work[9; 10]. Factors included are: history of overdose, an active mental health diagnosis, a history of positive tox screen for illicit drugs, an active or prior diagnosis of a substance use disorder, or multiple recent ED visits which included administration of an opioid.
- One-click access to the PDMP for all patients will be available as in other arms. If the EHR encounter includes records of a PDMP check, the BPA will be suppressed and not fire.
- As in Group 2 and 3, this is not a truly mandatory check and can be bypassed.

The exact messaging included in and format of the BPAs were determined based on the results of study 19-3063 and technical feasibility. For high-risk prescribing, each BPA will provide an alert and embedded link to action (“check the PDMP”), a reason (“your patient is at high risk due to XXX”) and a link to a website providing more information about the study, the logic used to fire the CDS and resources for prescribers such as the CDC Guidelines. No treatment recommendations will be made as the goal of the CDS is to encourage providers to make effective use of existing resources to inform their prescribing. BPAs will be designed to track provider use vs. bypass.

A series of silent alerts will be used to capture information about patient risks and provider PDMP usage over time. For Arms 2 and 3 as described above, an alert nearly identical to the study alert will fire but not be visible to the provider (2nd level in model). The silent alert will have the same PDMP and EHR criteria but will not filter out patients for whom the provider has already checked the PDMP (suppressed in provider alert). This will allow tracking of provider PDMP behavior change over time since we will have PDMP use due to BPA and PDMP by provider which suppresses BPAs. This is important to identify behavior change regarding PDMP use by providers.

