- Practices will be randomized at the time of activation of the CDS and will remain on study for 12 months.

Practices may be added during the course of the study. Follow up for patient outcomes will continue for 6 months following deactivation of the alerts.

CDS tools will be activated first in EDs, then for inpatient providers, and finally in ambulatory settings. This staged roll out will allow for identification and modification of system bugs and unanticipated problems, as well as allow for increased socialization of the tools and greater buy in by providers.

This study design is chosen for a combination of scientific and pragmatic concerns. This study is effectively an implementation of a novel CDS augmentation, such as would happen routinely in a non-research environment on a practice-by-practice basis. Therefore, to better mimic this real world situation, the most appropriate unit of randomization would be the practice/site. However, pragmatic concerns also inform the design, specifically:

- 1. Primary care:** Randomizing by practice will optimize the opportunities for provider education and reduce the risk of cross-group contamination if a single provider or practice treated multiple patients with similar risk patterns but received different CDS alerts. It also ensures that all members of a treatment team working with a single patient or single encounter receive the same information about that patient's risk stratification.
- 2. Hospital based:** The small number of EDs and hospitals, especially large EDs, relative to the number of randomization groups translates to a large risk of unbalanced groups. To address this issue, a smaller unit of randomization is appropriate specifically for EDs and hospital discharges. The authorizing provider is ultimately responsible for opioid prescribing and as such is most appropriate as a smaller unit. As residents work under a number of attending physicians, this will also prevent the development of overreliance on automated alerts in a physician in training, in order to minimize the chance of risk to clinical care.

Prior to CDS activation and at the time of activation, training materials will be shared with relevant sites and practices. These materials are included in Appendix #. A link to a provider feedback survey in REDCap will be included in order to collect standardized feedback from system users.

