Activation of the alert will be monitored using automated tracking within Epic which identifies providers and patients associated with alert firings. A key feature of the CDS is that the PDMP check must be "attested" to in order to suppress the CDS and prevent re-firing of the alerts, which is interruptive to the provider. This attestation is a workflow change for providers and is essential for CDS success. It can happen prior to prescription entry, in which case the alerts will not activate (suppression), or after activation of the alert.

In the event that providers are being "hit" with CDS alerts multiple times within the same encounter for a single patient because they miss the attestation step, an educational message with a link to the education website will be sent to the provider via email or EHR internal messaging systems to remind the provider to click the attestation button in order to prevent multiple firings. A weekly tally of messages sent will be retained, but no patient information will be retained. No provider will receive more than three educational reminders. The reminder will not include any patient information. This check is intended only to provide an additional personalized education step.

This is important because (1) dissemination of education about new CDS across all of UCHealth is challenging so we will miss providers and (2) we have concerns that if providers find the CDS to be a nuisance (due to a simple knowledge gap of not understanding the attestation requirement) they will not use the CDS.

Similarly, if a provider receives multiple alerts but does not access the PDMP in response, a reminder will be sent that checking the PDMP requires the same number of "clicks" as dismissing the alert and is considered best practice prior to prescribing. As with the contact

described above, these reminders will not contain any patient specific information and are designed as a personalized education step. No provider will receive more than three contacts in this way.

From initiation of educational messages until 9/20/2021, providers who receive one of the above educational messages will receive the message via email. Educational messages sent on or after 9/21/2021 will be sent via internal messaging within the EHR. This change in educational message delivery will allow for examination of best practices with providers.

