3. Description of use of the PDMP and study-associated BPAs, specifically monitoring
 - # of times PDMP activity/website is checked by site/practice/service, monthly, and specialty
 - Frequency of use of the PDMP one-click button per visit and per opioid prescription
 - Frequency of CDS and BPA trigger overall and per opioid prescription
 - Frequency of prescriptions for which the BPA would have fired but the prescriber had already checked the PDMP (look for change over time – do the BPAs lead to learning & change in prescriber behavior)
 - Number of times CDS alert fired, total and per visit (the alert is designed to only fire once during any encounter, thus the per visit rate will be <1)
 - Reviewed (via radio button or via alert)/unable to review/blank

- Resulted in signed Rx (reviewed/unable checked, signed prescription)
- Use of training tools and website. Identifying information on individuals accessing tools will not be recorded.
- Qualitative/semi-quantitative feedback from users as the CDS alerts are implemented

Patient specific measures will include:

- Number of controlled medication prescriptions, both within UCHealth and outside, based on PDMP data (including prescription details to include generic name, dosage, MMEs, days prescribed)
- Use of the PDMP by the prescriber prior to each controlled medication prescription written
- NarxCare risk score at the time of each prescription
- Number of providers/practices used for controlled substance prescriptions
- Number of pharmacies used for controlled substance prescriptions
- Diagnosis of any substance use disorder after the index visit date
- Accidental overdose of controlled substance after the index date (if data available)
- Patient demographics and clinical history characteristics

Educational outreach analysis: Alert firings for providers part of the educational outreach group will be analyzed for percent of non-compliant firings before outreach vs after as well as a comparison between the two different educational outreach efforts (email or EHR messaging system). Non-compliance is defined as 3 or more alerts for a single patient/encounter or >80% of firings closed using the comment/close option rather than using the PDMP link. Firings over time will be tracked as will changes in compliance before and after each outreach attempt. These data will be de-identified prior to reporting. Data will be examined for patterns based on demographics or work environment.

Calculation of sample size:

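### Whether the alerts change prescriber behaviour is to be read from a trend over time in pre-order PDMP checks, with no stated contrast to Arm 1, so an alert effect could not be told apart from a system-wide trend.

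*Combined protocol and SAP*

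**What the plan says.** Item 3 of the hospital system measures in Section IV.F tracks flagged prescriptions where the PDMP check came before the alert could fire. It is to be read as a change over time, under the question "do the BPAs lead to learning & change in prescriber behavior". The silent-alert text in Section IV.C gives the same rationale for the unsuppressed mirrors in Arms 2 and 3: "This will allow tracking of provider PDMP behavior change over time since we will have PDMP use due to BPA and PDMP by provider". It calls this important for identifying behaviour change.

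The other relevant statements are these:

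- **Breakdown of PDMP use.** Section IV.F, item 3, plans the number "of times PDMP activity/website is checked by site/practice/service, monthly, and specialty". Study arm is not in that line. It is listed in item 2, for prescription counts.
- **Role of Arm 1.** Section IV.C says "This control group will enable monitoring of the secular changes in rates of controlled medication prescription within the UCHealth system". The silent logic in Arm 1 is justified by the analysis of patient outcomes.
- **Figure 4.** The second-level row, which captures all PDMP use, is blank for Arm 1. It is also blank for Arm 4, where the third-level alert already mirrors the visible one. The third-level alert, an unsuppressed mirror of alert 14644, runs in all four arms.
- **Suppression.** Section IV.C says a check must be attested "in order to suppress the CDS and prevent re-firing of the alerts, which is interruptive to the provider".
- **After deactivation.** Section IV.C says "Follow up for patient outcomes will continue for 6 months following deactivation of the alerts".

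**The concern.** The question is causal and the stated method is a time trend. A trend within the alert arms contains whatever the alerts did plus whatever would have happened to PDMP checking anyway. Randomisation supplies the second quantity through Arm 1, but the plan does not say it will be used for this measure.

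The primary outcome does not fill the gap. It counts any check of a high-risk patient, so it combines checks prompted by the pop-up with checks the prescriber started unprompted. Only the second kind bears on whether prescribers have changed their own practice. At stake is what the trial can say about that change, not the primary result.

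**Working it through.** **Is there a figure to reproduce?** No. The plan gives no sample size, alpha, power, expected rate or drift for this measure. The check is a reading of the text plus an illustration whose inputs are assumed where marked.

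**Step 1. What each passage supplies for this measure.**

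| Place | Time trend | Contrast with Arm 1 for pre-order checks |
|---|---|---|
| IV.F, item 3 | yes | not stated |
| IV.C, silent alerts in Arms 2 and 3 | yes | not stated |
| IV.F, data table, provider-specific rate of PDMP use | yes, by provider | not stated |
| IV.F, item 2 | by month | by arm, but for prescription counts with a check annotation; not limited to flagged prescriptions or to checks made before the alert would fire |
| IV.C, Figure 4, level 3 | data available | data available in all four arms; no contrast stated |

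**Step 2. What the trend contains.** Let D be drift common to all arms, A the checking done only to avoid the pop-up, and L lasting change in habit.

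- Change within an alert arm = D + A + L
- Change in Arm 1 over the same months = D
- Difference while the alert is live = A + L

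Set L = 0 and assume D and A, in percentage points:

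| D | A | Within-arm change | Minus Arm 1 change |
|---|---|---|---|
| 2 | 0 | 2 + 0 = 2 | 2 − 2 = 0 |
| 5 | 0 | 5 + 0 = 5 | 5 − 5 = 0 |
| 5 | 5 | 5 + 5 = 10 | 10 − 5 = 5 |
| 10 | 0 | 10 + 0 = 10 | 10 − 10 = 0 |
| 10 | 10 | 10 + 10 = 20 | 20 − 10 = 10 |

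The contrast with Arm 1 removes D completely. It leaves A mixed with L.

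**Step 3. Could drift alone look convincing?** The plan states no test, so this is illustration only. The starting rate is p0 = 0.218, the adjusted check probability from the prior ED study (Section III). It is not this trial's pre-order rate. Compare an early and a late period in one alert arm, n flagged prescriptions each (assumed), two-sided 0.05, prescriptions treated as independent, A = L = 0, so p1 = p0 + D:

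P(significant) = Φ[(D − 1.96·se0)/se1], with se0 = √(2·p̄(1 − p̄)/n) and se1 = √([p0(1 − p0) + p1(1 − p1)]/n).

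For D = 0.05 and n = 2,000: p̄ = 0.243, se0 = 0.01356, se1 = 0.01354, so (0.05 − 1.96 × 0.01356)/0.01354 = 1.73 and Φ(1.73) = 0.958.

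| D | n = 500 | n = 2,000 | n = 10,000 |
|---|---|---|---|
| 0.01 | 0.057 | 0.115 | 0.397 |
| 0.02 | 0.114 | 0.325 | 0.921 |
| 0.05 | 0.453 | 0.958 | 1.000 |
| 0.10 | 0.947 | 1.000 | 1.000 |

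Clustering by provider would lower these probabilities. It would not change the bias of D points.

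**The case against.** The strongest reply is that this is one line in a list of descriptive monitoring items. Learning is neither a hypothesis (Section I) nor a primary or secondary outcome (Section IV.A), and no test, threshold or reporting rule is attached. That stands. A reader might infer that drift would be reported as learning; the documents support only that the two could not be told apart.

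Second, the control group is there to separate temporal from study effects (Section IV.E), Hypothesis 1 compares checking with those without the tool, and item 2 of the system measures would give a recorded-check rate by arm and month. This shows that the data and the intent exist. It does not supply a contrast for pre-order checks: the trend described in Section IV.E is in opioid prescribing, and item 2 does not isolate checks made before the alert would fire. The 12-month retrospective baseline does not settle it either. A before-and-after comparison still carries drift, and the silent alerts are not said to run before activation.

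Third, evidence that checking drifts is thin. The rise in searches reported in Section III accompanied one-click integration, which is an intervention. This stands, and it is why the drift figures above are labelled as assumptions.

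Fourth, a reader might infer that the trial must show persistence after the alerts are switched off, or must keep the silent alert running for the 6 months that follow. The documents do not support that. The protocol never asks whether the behaviour outlasts the alert, and Section IV.C treats attestation as an intended workflow change. Section IV.F counts every queried patient as a participant, so longer querying could add to the estimated 950,000.

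**Conclusion.** The point holds for this one descriptive measure. As written, a rise in pre-order PDMP checking in the alert arms cannot be attributed to the alerts, because the stated method is a time trend without an Arm 1 contrast. The error equals the drift in checking, point for point. Its size is unknown from the documents; the illustrations of 2 to 10 points are assumptions. The argument rests on Arm 1 sharing the same underlying trend, which randomisation within setting supports.

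The primary comparison with control is untouched. It would be too strong to say the trial cannot answer the question, because the data for the randomised contrast are already being captured. Even with that contrast, avoidance of the pop-up and lasting habit stay combined while the alert is live.

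**What to change.** In Section IV.F, replace the time-trend reading with the following:

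1. Report the pre-order PDMP check rate among prescriptions flagged by the common level 3 criteria (the mirror of 14644), by study arm and month since activation. Common criteria are needed because the second-level mirrors in Arms 2 and 3 use different triggers.
2. Compare with Arm 1 within each setting: Arms 2, 3 and 4 versus Arm 1 for ED and inpatient prescribers, and Arms 3 and 4 versus Arm 1 for ambulatory practices. Allow for clustering by the unit randomised. Base any statement about alert-driven change on this contrast.
3. Define a check by recorded PDMP access where available, not by attestation alone. Only the alert arms are prompted to attest, so an attestation-based rate would mix recording habits with checking.
4. Describe the result as behaviour change under a live alert.

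Optionally, if the per-prescription PDMP-use data listed under the patient-specific measures cover the existing 6-month follow-up, describe the same between-arm contrast after deactivation.

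The main cost is SAP wording and analysis time, since the level 3 alert already runs in all four arms. Step 3 depends on access records that can be linked to the order and timed against it; where they are missing, the limitation should be stated.

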Provider identifying information will be retained in order to determine the effectiveness of the educational outreach. Information retained will include alert firings (including multiple firings/patient) and provider actions over time. In order to better understand the environments in which educational intervention is most effective, provider specialty, primary work site, and basic demographic information (age, gender, race/ethnicity), will be obtained from within the EHR. Method of notification (email or internal messaging within the EHR) will also be tracked to compare provider behavioral changes between educational notifications. Provider work environment (Emergency Department, inpatient or ambulatory) will be determined based on study randomization lists. Data will be deidentified for analysis. Data on CDS and site performance will be monitored continuously during the course of the study (see attached file "Baseline data" for details of data monitored) via automated data extract built by ED Epic analytics team and monitored by study team. No identifiable data will be collected in order to protect confidentiality. De-identified extracts of these data may be exported from Epic to the UCDenver OneDrive system for CDS monitoring and analysis. Baseline data will be gathered retrospectively for the 12 months prior to first deployment of the CDS for each randomization unit. Providers who are not in the system for the baseline will be excluded from analysis.

Validation of the alerts

In order to ensure that the alerts are functioning properly prior to activation, up to 30 individual firings will be identified by study staff and EHR records of the patient will be checked to confirm that a controlled medication was prescribed and the risk criteria identified by the alert system are reflected in the medical record. Records of this validation will be maintained only by alert firing number. Identifying information associated with the alert will not be maintained once the alert firing is validated.

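### The plan assumes one alert per encounter but expects repeat firings elsewhere, so its per-visit alert rate and firing-based outreach measures depend on how often alerts repeat

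*Combined protocol and SAP*

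**What the plan says.** Section IV.F (Data Analysis Plan), in the list of measures of PDMP and alert use, includes the number of alert firings in total and per visit, and adds that "the alert is designed to only fire once during any encounter, thus the per visit rate will be <1". The same list has "Frequency of CDS and BPA trigger overall and per opioid prescription".

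Other current text expects repeats:

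- Section IV.C (Study Design and Research Methods) describes the PDMP check as one that providers have to attest "to in order to suppress the CDS and prevent re-firing of the alerts, which is interruptive to the provider". It plans educational messages for providers who are hit "with CDS alerts multiple times within the same encounter for a single patient because they miss the attestation step".
- Section IV.C also says of the outreach data: "Information retained will include alert firings (including multiple firings/patient) and provider actions over time".
- Section IV.F, under the educational outreach analysis, says: "Non-compliance is defined as 3 or more alerts for a single patient/encounter or >80% of firings closed using the comment/close option", as opposed to using the PDMP link.

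The outreach analysis is stated in firings: "Alert firings for providers part of the educational outreach group will be analyzed for percent of non-compliant firings before outreach vs after". It also compares the two delivery routes, email and EHR messaging. No section says how repeat firings within an encounter are to be combined, or which of several responses counts.

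**The concern.** An alert that fires at most once per encounter can never reach three alerts in that encounter. The once-only statement and the non-compliance rule therefore cannot both describe the same alert. The plan also draws a numerical conclusion from the once-only statement, so the conflict goes beyond wording.

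The analytic consequence lies in the unit. When firings are counted, an encounter contributes in proportion to how often its alert repeated. One of the two planned reminders is aimed at exactly that repetition. If it works, the denominator of the firing-based percentage changes after outreach, and the percentage can move although providers respond in the same share of encounters as before. A reader could then take fewer repeats for more PDMP use. Provider classification under the 80% branch, and the email versus EHR-message comparison, use the same unit.

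**Working it through.** **Inputs.** The documents give the once-only statement, the bound of 1, the three-or-more rule and the 80% threshold (all Section IV.F), and re-firing without attestation (Section IV.C). They give no share of visits with an alert, no number of firings per alerted visit and no breakdown of responses. All such values below are assumptions.

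**1. The plan's own figure.** Let q be the share of visits with at least one firing and m the mean number of firings per alerted visit. Then firings per visit = q × m. With m = 1 the rate equals q, which is below 1 whenever some visits have no alert. The bound follows from its premise.

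**2. The same rate with repeats.**

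| q | m = 1 | m = 1.5 | m = 2 | m = 3 | m at which the rate reaches 1 (1/q) |
|---|---|---|---|---|---|
| 0.05 | 0.05 | 0.075 | 0.10 | 0.15 | 20 |
| 0.20 | 0.20 | 0.30 | 0.40 | 0.60 | 5 |
| 0.50 | 0.50 | 0.75 | 1.00 | 1.50 | 2 |
| 0.80 | 0.80 | 1.20 | 1.60 | 2.40 | 1.25 |

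When alerts are rare the rate stays below 1, but it no longer equals q. When alerts are common it can pass 1.

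**3. Weight of one encounter.** Take 10 alerted encounters, one with 3 firings and nine with 1. The repeating encounter supplies 3/(9 + 3) = 3/12 = 25% of firings, against 1/10 = 10% of encounters.

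**4. The 80% branch.** An encounter counts as closed here if every firing in it was closed.

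- Upward: 10 alerted encounters, 7 closed and 3 answered with the PDMP link. Six of the 7 re-fire once and are closed again. By firing, (7 + 6)/(10 + 6) = 13/16 = 81.3%, which is flagged. By encounter, 7/10 = 70%, which is not. With 5 re-firing the share is 12/15 = 80%, not above the threshold, so 6 is the smallest number that tips this case.
- Downward: 20 alerted encounters, 17 closed with one firing each and 3 answered with the link, each firing twice with the link used both times. By firing, 17/(17 + 6) = 17/23 = 73.9%, which is not flagged. By encounter, 17/20 = 85%, which is.

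No encounter in either case reaches three alerts, so the other branch of the rule does not decide the label.

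**5. Before against after outreach.** Section IV.F does not say what makes a single firing non-compliant, so the closed share of firings is used here. In both periods 14 of 20 alerted encounters are closed and 6 are answered with the link at one firing each. Before outreach, 7 of the 14 re-fire once and are closed again; afterwards none do.

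- Before: (14 + 7)/(20 + 7) = 21/27 = 77.8%.
- After: 14/20 = 70%.
- Apparent fall: 7.8 percentage points. By encounter: 70% in both periods, no change.

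**The case against.** The strongest defence is that the once-only phrase states a design intention. The alert may be built to fire once when the workflow is followed, with repeats arising only from a missed click, and the reminders exist to deal with those. Reducing repeats is then a real aim of the outreach, and the three-or-more branch counts them on purpose. Much of this stands: that branch is not distorted by counting repeats, and a fall in repeats is a genuine result. It does not rescue the inference to a rate below 1, which needs the intention to hold in practice, and it does not supply a unit for the 80% branch or the outreach percentage.

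Four stronger readings are tempting, and the documents do not support them.

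- **That the bound of 1 is false.** It is only no longer guaranteed; with rare alerts it would still hold.
- **That any percentage per firing leans toward non-response.** Section IV.C attributes repeats to a missed attestation step and treats failure to open the PDMP as a separate problem with its own reminder. Repeats may be closed or answered with the link, so the direction cannot be fixed in advance.
- **That measured PDMP use is heavily understated.** One could take the 0.218 in Section III and let unchecked encounters fire three times, giving 0.218/(0.218 + 0.782 × 3) = 8.5%. But 0.218 is an adjusted probability from the previous study among patients who received an opioid prescription, and this plan does not explicitly define any PDMP-check measure per firing.
- **That the main result is affected.** Section IV.A defines the primary outcome per high-risk patient, and neither hypothesis in Section I rests on a firing count.

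Nor does a provider with five closed firings in one encounter show that the 80% branch mislabels anyone: the three-or-more branch already flags that provider.

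**Conclusion.** The point holds, at minor severity. The once-only statement conflicts with Section IV.C and with the non-compliance rule in Section IV.F. Firings per visit therefore cannot be read as the share of visits with an alert.

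The outreach percentage and the 80% branch give extra weight to encounters that re-fire, in a direction that depends on how repeats end. In the assumed examples the shift is 7.8 percentage points before against after, and about 11 points on the closed share in either direction (81.3% against 70%; 73.9% against 85%), enough to change a provider's label. These sizes illustrate the mechanism and are not estimates, since the plan gives no firing counts. The reach is system monitoring and the ancillary outreach analysis.

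**What to change.** 1. Reconcile Sections IV.C and IV.F on whether and when an alert can repeat within an encounter, and remove the inference from once-only firing to a rate below 1.
2. Use the alerted encounter as the unit for the alert rate (visits with at least one alert, divided by visits), for the 80% branch, and for the before/after and email versus EHR-message comparisons.
3. State which response counts when there are several firings. One option is to class an encounter as answered if the PDMP link was used at any firing, and as closed only if every firing was closed. This keeps the plan's contrast between closing the alert and using the link.
4. State the time window over which the 80% share is computed, and what the outreach percentage counts as non-compliant.
5. Keep the three-or-more branch, and report firings per alerted encounter as a separate measure, so that a reduction in repeats is shown as such.
6. Leave the unit of the primary outcome, high-risk patients, unchanged.

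The cost is a few sentences and a collapse of the firing log by encounter. The three-or-more rule already requires firings to be grouped by patient or encounter, so no new data are needed, and neither the alert logic nor care changes.
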